Stevens Johnson syndrome or toxic epidermal necrolysis, (any grade)	
Additional guidance for Stevens Johnson syndrome or toxic epidermal necrolysis:
 
 Withhold atezolizumab for suspected Stevens Johnson syndrome or toxic epidermal necrolysis. Confirm diagnosis by referring patient to a specialist (dermatologist, ophthalmologist or urologist as relevant) for evaluation and, if indicated, biopsy. Follow the applicable treatment and management guidelines above. If Stevens Johnson syndrome or toxic epidermal necrolysis, permanently discontinue atezolizumab.

^a Atezolizumab may be withheld for a longer period of time (i.e., >12 weeks after event onset) to allow for corticosteroids (if initiated) to be reduced to the equivalent of ≤ 10 mg/day oral prednisone. The acceptable length of the extended period of time must be based on assessment of benefit-risk by the investigator and in alignment with the protocol requirement for duration of treatment and documented by the investigator. Medical Monitor is available to advise as needed.

^b If corticosteroids have been initiated, they must be tapered over ≥ 1 month to the equivalent of ≤ 10 mg/day oral prednisone before atezolizumab can be resumed.

^c Resumption of atezolizumab may be considered in patients who are deriving benefit and have fully recovered from the immune-mediated event. The decision to rechallenge patients with atezolizumab should be based on investigator's assessment of benefit-risk and documented by the investigator (or an appropriate delegate). Medical Monitor is available to advise as needed..

J) Management Guidelines for Neurologic Disorders

Event	Management
Immune-mediated neuropathy, Grade 1	
 Continue atezolizumab. Investigate etiology
Immune-mediated neuropathy, Grade 2	
 Withhold atezolizumab for up to 12 weeks after event onset.^a Investigate etiology and refer patient to neurologist. Initiate treatment as per institutional guidelines. If event resolves to Grade 1 or better, resume atezolizumab.^b If event does not resolve to Grade 1 or better while withholding atezolizumab, permanently discontinue atezolizumab and contact Medical Monitor.^c
Immune-mediated neuropathy, Grade 3	
 Permanently discontinue atezolizumab and contact Medical Monitor.^c Refer patient to neurologist. Initiate treatment as per institutional guidelines.
Myasthenia gravis and Guillain-Barré syndrome (any grade)	
 Permanently discontinue atezolizumab and contact Medical Monitor.^c Refer patient to neurologist. Initiate treatment as per institutional guidelines. Consider initiation of corticosteroids equivalent to 1-2 mg/kg/day oral or IV prednisone.

^a Atezolizumab may be withheld for a longer period of time (i.e., >12 weeks after event onset) to allow for corticosteroids (if initiated) to be reduced to the equivalent of ≤ 10 mg/day oral prednisone. The acceptable length of the extended period of time must be based on assessment of benefit-risk by the investigator and in alignment with the protocol requirement for duration of treatment and documented by the investigator. Medical Monitor is available to advise as needed.

^b If corticosteroids have been initiated, they must be tapered over ≥ 1 month to the equivalent of ≤ 10 mg/day oral prednisone before atezolizumab can be resumed.

^c Resumption of atezolizumab may be considered in patients who are deriving benefit and have fully recovered from the immune-mediated event. The decision to rechallenge patients with atezolizumab should be based on investigator's assessment of benefit-risk and documented by the investigator (or an appropriate delegate). Medical Monitor is available to advise as needed.

K) Management Guidelines for Immune-Mediated Meningoencephalitis

Event	Management
Immune-mediated meningoencephalitis, all grades	
• Permanently discontinue atezolizumab and contact Medical Monitor.^a• Refer patient to neurologist. Initiate treatment with corticosteroids equivalent to 1-2 mg/kg/day IV methylprednisolone and convert to 1-2 mg/kg/day oral prednisone or equivalent upon improvement.• If event does not improve within 48 hours after initiating corticosteroids, consider adding an immunosuppressive agent.• If event resolves to Grade 1 or better, taper corticosteroids over \geq 1 month

^a Resumption of atezolizumab may be considered in patients who are deriving benefit and have fully recovered from the immune-mediated event. The decision to rechallenge patients with atezolizumab should be based on investigator's assessment of benefit-risk and documented by the investigator (or an appropriate delegate). Medical Monitor is available to advise as needed.

L) Management Guidelines for Renal Events

Event	Management
Renal event, Grade 1	
 Continue atezolizumab. Monitor kidney function closely, including creatinine and urine protein, until values resolve to within normal limits or to baseline values.
Renal event, Grade 2	
 Withhold atezolizumab for up to 12 weeks after event onset.^a Refer patient to renal specialist. Initiate treatment with corticosteroids equivalent to 1-2 mg/kg/day oral prednisone. If event resolves to Grade 1 or better, resume atezolizumab.^b If event does not resolve to Grade 1 or better while withholding atezolizumab, permanently discontinue atezolizumab and contact Medical Monitor.^c
Renal event, Grade 3 or 4	
 Permanently discontinue atezolizumab and contact Medical Monitor. Refer patient to renal specialist and consider renal biopsy. Initiate treatment with corticosteroids equivalent to 1-2 mg/kg/day oral prednisone. If event does not improve within 48 hours after initiating corticosteroids, consider adding an immunosuppressive agent. If event resolves to Grade 1 or better, taper corticosteroids over \geq 1 month.

^a Atezolizumab may be withheld for a longer period of time (i.e., >12 weeks after event onset) to allow for corticosteroids (if initiated) to be reduced to the equivalent of ≤ 10 mg/day oral prednisone. The acceptable length of the extended period of time must be based on assessment of benefit-risk by the investigator and in alignment with the protocol requirement for duration of treatment and documented by the investigator. Medical Monitor is available to advise as needed.

^b If corticosteroids have been initiated, they must be tapered over ≥ 1 month to the equivalent of ≤ 10 mg/day oral prednisone before atezolizumab can be resumed.

^c Resumption of atezolizumab may be considered in patients who are deriving benefit and have fully recovered from the immune-mediated event. The decision to rechallenge patients with atezolizumab should be based on investigator's assessment of benefit-risk and documented by the investigator (or an appropriate delegate). Medical Monitor is available to advise as needed.

M) Management Guidelines for Immune-Mediated Myositis

Event	Management
Immune-mediated myositis, Grade 1	
 Continue atezolizumab. Refer patient to rheumatologist or neurologist. Initiate treatment as per institutional guidelines.
Immune-mediated myositis, Grade 2	
 Withhold atezolizumab for up to 12 weeks after event onset and contact Medical Monitor. Refer patient to rheumatologist or neurologist. Initiate treatment as per institutional guidelines. Consider treatment with corticosteroids equivalent to 1-2 mg/kg/day IV methylprednisolone and convert to 1-2 mg/kg/day oral prednisone or equivalent upon improvement. If corticosteroids are initiated and event does not improve within 48 hours after initiating corticosteroids, consider adding an immunosuppressive agent. If event resolves to Grade 1 or better, resume atezolizumab.^b If event does not resolve to Grade 1 or better while withholding atezolizumab, permanently discontinue atezolizumab and contact Medical Monitor.^c
Immune-mediated myositis, Grade 3	
 Withhold atezolizumab for up to 12 weeks after event onset and contact Medical Monitor. Refer patient to rheumatologist or neurologist. Initiate treatment as per institutional guidelines. Respiratory support may be required in more severe cases. Initiate treatment with corticosteroids equivalent to 1-2 mg/kg/day IV methylprednisolone, or higher-dose bolus if patient is severely compromised (e.g., cardiac or respiratory symptoms, dysphagia, or weakness that severely limits mobility); convert to 1-2 mg/kg/day oral prednisone or equivalent upon improvement. If event does not improve within 48 hours after initiating corticosteroids, consider adding an immunosuppressive agent. If event resolves to Grade 1 or better, resume atezolizumab.^b If event does not resolve to Grade 1 or better while withholding atezolizumab, permanently discontinue atezolizumab and contact Medical Monitor.^c For recurrent events, treat as a Grade 4 event.
Immune-mediated myositis, Grade 4	
 Permanently discontinue atezolizumab and contact Medical Monitor.^c Refer patient to rheumatologist or neurologist. Initiate treatment as per institutional guidelines. Respiratory support may be required in more severe cases. Initiate treatment with corticosteroids equivalent to 1-2 mg/kg/day IV methylprednisolone, or higher-dose bolus if patient is severely compromised (e.g., cardiac or respiratory symptoms, dysphagia, or weakness that severely limits mobility); convert to 1-2 mg/kg/day oral prednisone or equivalent upon improvement. If event does not improve within 48 hours after initiating corticosteroids, consider adding an immunosuppressive agent. If event resolves to Grade 1 or better, taper corticosteroids over ≥ 1 month.

^a Atezolizumab may be withheld for a longer period of time (i.e., >12 weeks after event onset) to allow for corticosteroids (if initiated) to be reduced to the equivalent of ≤ 10 mg/day oral prednisone. The acceptable length of the extended period of time must be based on the assessment of benefit-risk by the investigator and in alignment with the protocol requirement for duration of treatment and documented by the investigator. Medical Monitor is available to advise as needed.

^b If corticosteroids have been initiated, they must be tapered over ≥ 1 month to the equivalent of ≤ 10 mg/day oral prednisone before atezolizumab can be resumed.

^c Resumption of atezolizumab may be considered in patients who are deriving benefit and have fully recovered from the immune-mediated event. The decision to rechallenge patients with atezolizumab should be based on investigator's assessment of benefit-risk and documented by the investigator (or an appropriate delegate). Medical Monitor is available to advise as needed.

N) Hemophagocytic Lymphohistiocytosis and Macrophage Activation Syndrome

Event	Management
Suspected HLH or MAS	
• Permanently discontinue atezolizumab and contact Medical Monitor.• Consider patient referral to hematologist.• Initiate supportive care, including intensive care monitoring if indicated per institutional guidelines.• Consider initiation of IV corticosteroids, an immunosuppressive agent, and/or anti-cytokine therapy.• If event does not respond to treatment within 24 hours, contact Medical Monitor and initiate treatment as appropriate according to published guidelines (La Rosée 2015; Schram and Berliner 2015; La Rosée et al. 2019).• If event resolves to Grade 1 or better, taper corticosteroids over ≥ 1 month.

HLH hemophagocytic lymphohistiocytosis; IVintravenous; MAS macrophage activation syndrome.

O) Severe skin adverse reactions related to the immune system (SCARS)

Event	Management
Skin reaction Grade 3	
Temporary discontinue atezolizumab and start corticosteroid treatment with prednisone 1-2 mg/kg/day or equivalent.Treatment with atezolizumab can be resumed if the event improves to \leq Grade 1 in 12 weeks, and corticosteroids have been reduced to \leq 10 mg of prednisolone or equivalent per day.
Skin reaction Grade 4	
Permanently discontinue atezolizumab and start corticosteroid treatment.
Stevens-Johnson syndrome (SJS) and toxic epidermal necrolysis (TEN)	
Temporary discontinue atezolizumab and contact Medical Monitor for confirmation.If SJS or NET is confirmed, atezolizumab should be permanently discontinued.Caution should be exercised when considering the use of atezolizumab in a patient who has previously had serious or life-threatening skin adverse reactions with prior treatment with other immunostimulatory anticancer drugs.

SJS Stevens-Johnson syndrome; TEN Toxic epidermal necrolysis.

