There may be significant overlap in signs and symptoms of IRRs and CRS, and in recognition of the challenges in clinically distinguishing between the two, consolidated guidelines for the medical management of IRRs during Cycle 1 and CRS are provided in Appendix 1.

Severe COVID-19 appears to be associated with a cytokine-release syndrome (CRS) involving the inflammatory cytokines interleukin (IL)-6, IL-10, IL-2, and interferon-(Merad and Martin 2020). If a patient develops suspected CRS during the study, a differential diagnosis should include COVID-19, which should be confirmed or refuted through assessment of exposure history, appropriate laboratory testing, and clinical or radiologic evaluations per investigator judgment. If a diagnosis of COVID-19 is confirmed, the disease should be managed as per local or institutional guidelines.

8) Pancreatic Events

Symptoms of abdominal pain associated with elevations of amylase and lipase, suggestive of pancreatitis, have been associated with the administration of atezolizumab. The differential diagnosis of acute abdominal pain should include pancreatitis. Appropriate work-up should include an evaluation for ductal obstruction, as well as serum amylase and lipase tests. Management guidelines for pancreatic events, including pancreatitis, are provided in Appendix 1.

9) Dermatologic Events

Treatment-emergent rash has been associated with atezolizumab. The majority of cases of rash were mild in severity and self-limited, with or without pruritus. Although uncommon, cases of severe cutaneous adverse reactions such as Stevens-Johnson syndrome and toxic epidermal necrolysis have been reported with atezolizumab. A dermatologist should evaluate persistent and/or severe rash or pruritus. A biopsy should be considered unless contraindicated. Management guidelines for dermatologic events are provided in Appendix 1.

10) Neurologic Disorders

Myasthenia gravis and Guillain-Barré syndrome have been observed with single-agent atezolizumab. Patients may present with signs and symptoms of sensory and/or motor neuropathy. Diagnostic work-up is essential for an accurate characterization to differentiate between alternative etiologies. Management guidelines for neurologic disorders are provided in Appendix 1.

11) Immune-Mediated Meningoencephalitis

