More information provided in Appendix 1.

15) Severe Cutaneous Adverse Reactions (SCARs)

SCARs are a heterogeneous group of immunologically mediated drug eruptions. Although rare, these events are potentially fatal, and mainly constituted by erythema multiforme, acute generalised exanthematous pustulosis, Stevens-Johnson syndrome (SJS), Toxic Epidermal Necrolysis (TEN) and drug rash with eosinophilia and systemic symptoms (DRESS). As per epidemiology data, the incidence of SJS and TEN ranges from 0.8 to 5.3 and 1.2 to 6 per million person-years respectively.

The following recommendations should be followed:

- For suspected SCARs the patients should be referred to a dermatologist for further diagnosis and management
- Atezolizumab should be withheld for patients with suspected SJS or TEN
- Atezolizumab should be permanently withdrawn for any grade confirmed SJS or TEN
- Caution should be used when considering the use of atezolizumab in a patient who has previously experienced a severe or life-threatening skin adverse reaction on prior treatment with other immune-stimulatory anticancer agents.

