^a Atezolizumab may be withheld for a longer period of time (i.e., >12 weeks after event onset) to allow for corticosteroids (if initiated) to be reduced to the equivalent of ≤ 10 mg/day oral prednisone. The acceptable length of the extended period of time must be based on assessment of benefit-risk by the investigator and in alignment with the protocol requirement for duration of treatment and documented by the investigator. Medical Monitor is available to advise as needed.

^b If corticosteroids have been initiated, they must be tapered over ≥ 1 month to the equivalent of ≤ 10 mg/day oral prednisone before atezolizumab can be resumed.

^c Resumption of atezolizumab may be considered in patients who are deriving benefit and have fully recovered from the immune-mediated event. The decision to rechallenge patients with atezolizumab should be based on investigator's assessment of benefit-risk and documented by the investigator (or an appropriate delegate). Medical Monitor is

available to advise as needed.

I) Management Guidelines for Dermatologic Events

Event	Management
Dermatologic event, Grade 1	
 Continue atezolizumab. Consider treatment with topical corticosteroids and/or other symptomatic therapy (e.g., antihistamines).
Dermatologic event, Grade 2	
 Continue atezolizumab. Consider patient referral to dermatologist for evaluation and, if indicated, biopsy. Initiate treatment with topical corticosteroids. Consider treatment with higher-potency topical corticosteroids if event does not improve. If unresponsive to topical corticosteroids, consider oral prednisone 0.5 mg/kg/day.
Dermatologic event, Grade 3	
 Withhold atezolizumab for up to 12 weeks after event onset.^a Refer patient to dermatologist for evaluation and, if indicated, biopsy. Initiate treatment with corticosteroids equivalent to 10 mg/day oral prednisone, increasing dose to 1-2 mg/kg/day if event does not improve within 48-72 hours. If event resolves to Grade 1 or better, resume atezolizumab.^b If event does not resolve to Grade 1 or better while withholding atezolizumab, permanently discontinue atezolizumab and contact Medical Monitor.^c
Dermatologic event, Grade 4	
 Permanently discontinue atezolizumab and contact Medical Monitor.^c

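### Appendix 1 gives inconsistent starting steroid doses for a Grade 3 severe cutaneous adverse reaction: table O appears meant to govern, but no sentence says so and table I's SJS/TEN row points elsewhere

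*Combined protocol and SAP*

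**What the plan says.** Appendix 1, table I (dermatologic events), Grade 3, withholds atezolizumab, refers the patient to a dermatologist and adds: "Initiate treatment with corticosteroids equivalent to 10 mg/day oral prednisone, increasing dose to 1-2 mg/kg/day if event does not improve within 48-72 hours". Its separate SJS/TEN row, for any grade, states no steroid dose and says: "Follow the applicable treatment and management guidelines above".

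Appendix 1, table O (SCARs), Grade 3, says: "Temporary discontinue atezolizumab and start corticosteroid treatment with prednisone 1-2 mg/kg/day or equivalent". Its Grade 4 row says: "Permanently discontinue atezolizumab and start corticosteroid treatment", with no dose. Its SJS/TEN row also has no dose and says: "Temporary discontinue atezolizumab and contact Medical Monitor for confirmation".

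In section 7.2.3, item 9 covers dermatologic events, mentions SJS and TEN, and ends: "Management guidelines for dermatologic events are provided in Appendix 1". Item 15 describes SCARs: "Although rare, these events are potentially fatal, and mainly constituted by erythema multiforme, acute generalised exanthematous pustulosis, Stevens-Johnson syndrome (SJS", with TEN and DRESS completing the list. It also says: "For suspected SCARs the patients should be referred to a dermatologist for further diagnosis and management". Item 15 gives no steroid dose and cites no table.

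**The concern.** A Grade 3 case of erythema multiforme, acute generalised exanthematous pustulosis or DRESS is a dermatologic event of Grade 3, so it meets table I's row label. It is also a SCAR with a Grade 3 skin reaction, so it meets table O's. The two rows start treatment at different doses. A site that opens table I first and follows it as written would give 10 mg/day and wait 48-72 hours before reaching the dose that table O gives at once.

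The protocol itself treats these reactions as potentially fatal, and Table 3 in section 9.4 lists severe cutaneous reactions among the adverse events of special interest. The starting dose should not depend on which table a site happens to consult.

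**Working it through.** **Rows side by side (Appendix 1)**

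| Row | Table I | Table O |
|---|---|---|
| Grade 3 | 10 mg/day, then 1-2 mg/kg/day if no improvement in 48-72 hours | 1-2 mg/kg/day from the start |
| Grade 4 | No steroid instruction | Start steroids, no dose |
| SJS/TEN | No dose; refers to the guidance above it | No dose; contact the Medical Monitor |

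Two express starting doses stand against each other only in the Grade 3 rows. For SJS/TEN the conflict is indirect. Table I's row leads back to its own grade rows, so a Grade 3 case arrives at 10 mg/day. In table O, 1-2 mg/kg/day has to be borrowed from the Grade 3 row.

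**Is there a rule of precedence?**

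- The general text of 7.2.3 calls for steroids according to severity, with no dose and no ranking of tables.
- Item 9 points to Appendix 1 without naming a table. Item 15 names none.
- Section 9.4 refers to the atezolizumab Investigator's Brochure, which is not among the documents.
- The protocol's table of contents lists the dermatologic guidelines under Appendix 1. Its Appendix 1 list ends at myositis, so table O has no entry.

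None of these ranks the two tables.

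**Size of the gap**

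The documents give no body weight, so 60-80 kg is assumed.

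- Weight at which the doses coincide: 10 mg / 1 mg/kg = 10 kg; 10 mg / 2 mg/kg = 5 kg. They therefore differ for any adult.
- Table O daily dose: 60 x 1 = 60 mg to 80 x 2 = 160 mg.
- Ratio to table I: 60/10 = 6 to 160/10 = 16.
- Over 48 hours (2 daily doses): table I gives 20 mg and table O 120-320 mg, a difference of 100-300 mg.
- Over 72 hours (3 daily doses): table I gives 30 mg and table O 180-480 mg, a difference of 150-450 mg.

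With a wider assumed range of 50-100 kg, table O gives 50-200 mg/day, 5 to 20 times table I.

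**The case against.** The strongest reply is that the layout already answers the question. The 15 items of section 7.2.3 and tables A to O of Appendix 1 run in the same order: item 9 corresponds to table I, and item 15 to table O. Item 15's advice on SJS/TEN (hold on suspicion, stop permanently if confirmed, take care after earlier severe skin reactions) recurs in table O. Table I never names erythema multiforme, acute generalised exanthematous pustulosis or DRESS. This stands, and it makes table O the better-supported reading for those three. It remains an inference, and table I's SJS/TEN row works against it.

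The main safety actions also agree. Both Grade 3 rows hold atezolizumab and start steroids. Every place that deals with SJS/TEN holds on suspicion and stops on confirmation. Item 15 sends every suspected SCAR to a dermatologist, and table O adds Medical Monitor contact for SJS/TEN. These steps reduce the risk but do not tell a site which dose to start.

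The events are rare. Item 15 gives incidences of 0.8-5.3 (SJS) and 1.2-6 (TEN) per million person-years, and the trial plans 54 to 144 patients. Those rates are not specific to atezolizumab and do not cover the other SCARs, so they support rarity without giving an expected count.

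**Conclusion.** The inconsistency is real and should be corrected, but it is narrow. It concerns the starting steroid dose at Grade 3 when the skin reaction is a SCAR. The 6- to 16-fold gap rests on the assumed 60-80 kg; that the doses differ for any adult does not.

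A reader might infer more than the documents support:

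- *That the protocol gives no indication which table governs.* It does, through the parallel order and the shared content of item 15 and table O. What is missing is an explicit rule.
- *That SJS/TEN has two stated doses.* Neither SJS/TEN row states one.
- *That table I's dose is wrong for every Grade 3 rash.* A Grade 3 event that is not a SCAR belongs under table I and is not in question here.
- *That patients will in practice be under-treated.* Specialist referral may settle the dose, and whether the Investigator's Brochure does so cannot be checked here.
- *That the trial's results are at risk.* The response rate endpoint, the Simon decision rule and the analysis sets are unaffected.

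**What to change.** Make three wording changes:

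1. Add to Appendix 1: *Table O governs any suspected or confirmed SCAR (section 7.2.3, item 15); table I governs all other dermatologic events.*
2. In table I's SJS/TEN row, replace the reference to the guidance above it with a reference to table O.
3. Cite table O from items 9 and 15 of section 7.2.3.

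Whether table O's SJS/TEN and Grade 4 rows should state a steroid dose is a clinical decision for the sponsor's medical team; neither row supplies a figure to carry over. The difference between the 42-day hold in section 7.2.2 and the 12-week holds in Appendix 1 is a separate matter that runs through the appendix, and it is not part of this point.

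The cost is an edit to Appendix 1 and section 7.2.3, with no added data, visits or patients.
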